7.3.2 Handling of Missing Data For Safety Evaluations

Adverse Event (AE) Summaries

With respect to summaries of AEs, only AEs that were treatment emergent will be tabulated. Treatment-emergent is defined as AEs with start date \geq date of first treatment administration.

- 1) If AE start date is completely missing, the date of first treatment administration will be taken as the start date of the event.
- 2) If AE start date is partially missing:
 - a. If the day part of the start date is missing, the start date will be estimated to be equal to the date of first treatment administration, provided the start month and year are the same as the date of first treatment administration and the stop date either after the

date of first treatment administration or completely missing. Otherwise, the AE will be assumed to have started on the first day of the month (01/MMM/YYYY)

- b. If the month part of the start date is missing, the start month will be estimated to be equal to the month of the date of first treatment administration or the following month after the month of the date of first treatment administration depending on the day part of the start date provided that the start year is the same as the year of date of first treatment administration and the stop date is either after date of first treatment administration or completely missing. Otherwise, the AE will be assumed to have started on the first month of the year (DD/Jan/YYYY)
- c. If both the day and month parts of the start date are missing, the start date will be estimated to be equal to the date of first treatment administration, provided the start year is the same as year of date of first treatment administration and the stop date is either after the date of first treatment administration or completely missing. Otherwise, the AE will be assumed to have started on first day and first month of the year (01/Jan/YYYY)
- d. If all day, month and year parts of the start date are missing, the start date will be estimated to be equal to the date of first treatment administration (and thus treatment emergent) provided that the stop date is either after the date of first treatment administration or completely missing. Otherwise, the start date will be estimated to be the first day of the same year as the stop date.

3) If AE stop date is partially or completely missing:

- a. If only the day portion of the stop date is unknown, the day will be assumed to be last date of the month (e.g., ??-Jan-2004 will be treated as 31-Jan-2004).
- b. If both the day and month of stop date are unknown, the event will be assumed to have ceased on the last day of the year (e.g., ??-??-2004 will be treated as 31-Dec-2004).

- c. If the stop date is completely missing, the event will be assumed to be “Ongoing”.

Concomitant medications (CM) Summaries

- 1) If CM start date is completely missing then the date of first treatment administration will be taken as the start date of the medication
- 2) If CM start date is partially missing:
 - a. If the Day part of the start date is missing, the CM will be assumed to have started on the first day of the month (01/MMM/ YYYY)
 - b. If the month part of the start date is missing, the CM will be assumed to have started on the first month of the year (dd/Jan/ YYYY)
 - c. If both the day and month parts of the start date are missing, the CM will be assumed to have started on first day and first month of the year (01/Jan/ YYYY)

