6.2.6. Adverse Events and Serious Adverse Events

Adverse events will be collected from the time the subject signs an informed consent through the Follow-up visit.

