6.2.6.1. Definition of Adverse Events

An AE is defined as any untoward medical occurrence in a subject administered a pharmaceutical product during the course of a clinical investigation. An AE can therefore be any unfavorable and unintended sign, symptom, or disease temporally associated with the use of an investigational product, whether or not thought to be related to the investigational product.

Subjects will be monitored throughout the study for AEs. Monitoring for treatment-emergent AEs will begin as soon as the subject is dosed. All AEs must be followed until they are resolved or stabilized, or until all attempts to determine resolution of the event are exhausted. The investigator should use their discretion in ordering additional tests as necessary to monitor the progress of such events.

An AE may be:

- A new illness, not documented in the subject's medical history;
- Worsening of a concomitant illness;
- An effect of the study medication; it could be an abnormal laboratory value, as well as a significant shift from baseline within normal range which the qualified investigator or medical qualified designate considers to be clinically important;
- A combination of two or more of these factors.

Surgical procedures themselves are not AEs. They are therapeutic measures for conditions that required surgery. The condition for which the surgery is required is an AE, if it occurs or is detected during the study period. Planned surgical measures permitted by the clinical study protocol and the condition(s) leading to these measures are not AEs, if the condition(s) was (were) known before the start of study treatment. In the latter case, the condition should be reported as medical history.

Subjects will be monitored throughout the study for AEs. All AEs must be followed until they are resolved or stabilized, or until all attempts to determine resolution of the event are exhausted. The investigator should use his/her discretion in ordering additional tests as necessary to monitor the progress of such events.

Adverse events reported prior to dose administration will be recorded as part of the subject's medical history.

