6.2.6.8. Adverse Event Recording and Reporting

Adverse events will be recorded throughout the study in the source documents and in the CRFs.

If known, the diagnosis should be recorded, in preference to the listing of individual signs and symptoms. Adverse event reporting for each subject starts when the subject signs the informed consent and continues at all subsequent visits through the Follow up Visit. Any preexisting conditions that are detected as part of the screening procedures will need to be reported in the medical history and not as an AE.

The investigator will rate AEs for seriousness, intensity, causality, action taken, and outcome as described in the previous sections.

Expedited reporting is required for serious unexpected adverse drug reactions. Fatal or life-threatening unexpected drug reactions must be reported by the Sponsor to regulatory agencies no more than 7 days after the Sponsor's first knowledge of the reaction; followed by as complete a report as possible within 8 additional days. Unexpected drug reactions must be reported no later than 15 days after the Sponsor's first knowledge of the reaction. In order to comply with these requirements, the investigator or delegate must inform the Sponsor immediately upon occurrence of any SAE. The site will complete the SAE Report Form as thoroughly as possible and fax it to Insys within 24 hours of the investigators first knowledge of the event.

Sponsor contact information is listed below:

[REDACTED]
[REDACTED]
Insys Development Company, Inc.

Email: [REDACTED]

Telephone: [REDACTED]

These SAE reports must contain the following information:

- A. Study name/number
- B. Study drug
- C. Investigator details (name, phone, fax, e-mail)
- D. Subject number
- E. Subject initials
- F. Subject demographics
- G. Clinical event
 - 1) Description
 - 2) Date of onset

- 3) Treatment (drug, dose, dosage form)
 - 4) Adverse event relationship to study drug
 - 5) Action taken regarding study drug in direct relationship to the AE
- H. If the AE was fatal or life-threatening
- I. Cause of death (whether or not the death was related to study drug)
- J. Autopsy findings (if available)

The Sponsor or its representative will be responsible for notification to regulatory agencies.

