7.3.1. Pre-randomization

On Day 1, the regional anesthetic infusion will be discontinued at approximately 3:00 AM. Thereafter, when subjects request pain medication, they will be asked to rate their pain intensity using an 11-point (0-10) Numeric Rating Scale (NRS). During the 9-hour period after discontinuation of the anesthetic block, subjects who experience a pain intensity rating of ≥ 4 on the NRS are eligible to be enrolled in the study. Subjects whose pain intensity ratings do not meet the minimum entry criteria within 9 hours after discontinuation of the regional anesthesia will not be eligible for enrollment and will receive routine postoperative care at the investigator's discretion. Pulse oximetry will be monitored continuously after the procedure as a safety measure.

When a subject's pain meets the pain intensity entry criteria (≥ 4 on the NRS), he or she will be eligible to begin the Treatment Period and will be randomized.

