7.3.2. Post-randomization

1. Measure vital signs (resting blood pressure, heart rate, respiratory rate, and oral body temperature) immediately before and 1 hour after the first dose of study drug on Day 0, then immediately before and 1 hour after the 24-hour and 40-hour doses, and at 48 hours.
2. Perform a 12-lead ECG before the first dose of study drug, and then at 90 minutes and 12, 24, and 48 hours after Time 0.
3. Pulse oximetry will be recorded at selected times, including baseline before Time 0 and at 90 minutes and 12, 24, and 48 hours after Time 0 (Tmax).
4. The subject is to record pain intensity (numerical rating scale) in the inpatient subject diary at Baseline before the first dose of study drug (Day 1). Thereafter, the subject is to record pain intensity and pain relief (5-point categorical scale) assessments at the following time points:
 - a. At 2.5, 5, 15, 30, and 45 minutes and 1, 1.5, 2, 3, 4, 5, 6, 7, 8, 12, 16, 20, 24, 32, 40 and 48 hours after Time 0, and immediately before each use of rescue analgesia.
 - b. At Early Withdrawal if a subject discontinues prematurely.
5. Administer the first dose of study drug within 9 hours (\pm 10 minutes) after the anesthetic block has been discontinued when a subject's pain intensity is ≥ 4 on the 11-point (0-10) NRS. Study drug will be administered from Time 0 through 48 hours within 10-minute windows.
6. Start stopwatches as soon as the first dose of study drug is administered. Stopwatches should be discontinued if the subject has not stopped them by the time of the second IP dose or first use of rescue medication (whichever occurs first).
7. Perform an oral cavity examination prior to and one hour after first dose.
8. Record concomitant medications.
9. Record AEs.
10. Subjects will complete a subject's global evaluation of study drug at the end of the treatment period (Day 3) before discharge from the study site or immediately before ET if a subject discontinues prematurely.
11. Dispense outpatient pain medication and an outpatient subject diary before discharge from the study on Day 3 (approximately 72 hours after completion of surgery).

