8.2.4 Adverse Events

Adverse events will be classified by system organ class (SOC) and preferred term (PT) according to the most recent MedDRA dictionary (Version 19.1 or higher).

All adverse events that occur on or after the date of first administration of clinical trial treatment until the end of study procedures are completed will be listed and summarized, using frequency

counts and percentages, by treatment group.

- Overall (*i.e.*, regardless of severity or relationship to treatment)
- By severity grade (mild, moderate, severe,)
- By relationship to clinical trial treatment (definitely related, probably related, possibly related, unlikely related, not related)

Unless otherwise specified, at each level of subject summarization, a subject will be counted only once. If there is more than one occurrence of an event, the event of the worst severity or the worst-case relationship category will be summarized.

AEs leading to premature discontinuation of clinical trial treatment, AEs of special interest, AEs that lead to study discontinuation, AEs that lead to death and Serious Adverse Events (SAEs) will also be summarized by treatment group and relationship. Adverse Events leading to premature discontinuation of clinical trial treatment will be defined as any adverse event with an Action Taken equal to “study drug discontinued” or “drug withdrawn”.

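### The SAP classifies treatment-emergent AEs by calendar date, so AE records with onset in the roughly 3 to 12 pre-dose hours of Day 1 would count as TEAEs

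*SAP*

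**What the plan says.** The SAP states the rule twice, both times by date. In 7.3.2, "Treatment-emergent is defined as AEs with start date" on or after the date of first treatment administration. In 8.2.4, "All adverse events that occur on or after the date of first administration of clinical trial treatment" are listed and summarized by arm. Neither section uses clock time.

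The protocol ties the start to the dose itself (6.2.6.1): "Monitoring for treatment-emergent AEs will begin as soon as the subject is dosed". Its AE summaries are restricted to TEAEs (8.5.4.1), so the definition decides what is tabulated.

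On events before the first dose, the protocol gives two messages. Section 6.2.6.1 says "Adverse events reported prior to dose administration will be recorded as part of the" subject's medical history. Section 6.2.6 says "Adverse events will be collected from the time the subject signs an informed consent through the Follow-up visit", and 6.2.6.8 says "Adverse event reporting for each subject starts when the subject signs the informed consent". Section 7.2.1 records AEs before surgery, and Table 2 marks AE assessment on Day 0 and in the pre-dose baseline column of Day 1.

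Timing comes from Protocol 7.3.1, "On Day 1, the regional anesthetic infusion will be discontinued at approximately 3:00 AM", and 7.3.2, "Administer the first dose of study drug within 9 hours" (± 10 minutes) of stopping the block. Section 4.4 places randomization on Day 1.

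**The concern.** A date rule does little harm when dosing happens early in the day or few events are expected before it. Here the dosing date opens with early postoperative hours: the block is still running until about 03:00, then it wears off and pain returns. Hydrocodone/acetaminophen is permitted until the infusion stops (Protocol 4.8 and 7.2.2). Nausea, vomiting and somnolence, which the protocol lists as fentanyl effects (1.5), could arise in these hours without any study drug. A date comparison cannot tell them from the same events after dosing.

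Safety against placebo is a secondary objective (Protocol 2.2), and TEAE incidence is the first-listed safety endpoint (Protocol 8.2, SAP 3.2). Adding events that precede the drug to every arm blurs that comparison.

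**Working it through.** **Pre-dose time on the dosing date.** Take "On Day 1, the regional anesthetic infusion will be discontinued at approximately 3:00 AM" as 03:00 and add the wait for the first dose.

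- Minimum: 3 h + 0 h = 3 h, and 3/24 = 12.5% of the calendar day.
- Maximum: 3 h + 9 h + 10 min = 12 h 10 min, and 12.17/24 = 50.7% of the day.
- If the stop time were anywhere from 02:00 to 04:00 (assumption), the range would be 2 to 13 h, ignoring the 10-minute window.

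Protocol 6.2.3, 7.3.2 (item 1) and Table 2 footnote d mention a first dose on Day 0 for vital signs. Sections 4.4, 6.1.1 and 7.3.1 and the Table 2 columns place it on Day 1, which is used here.

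**Which records are affected.**

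- Events with onset on Day 0 fail the date rule and are not affected.
- Events with onset on the dosing date before the dose, but reported after it, are counted as TEAEs. The medical-history sentence in 6.2.6.1 does not reach them, because it depends on when the event is reported.
- Events with onset and report before the dose are counted only if sites record them as AEs, which the protocol leaves in conflict.
- Hydrocodone/acetaminophen is allowed only until the infusion stops, so on the dosing date it can be given only between about 00:00 and 03:00.
- Exclusions 2 and 25 (Protocol 3.2.2) remove confounding surgical complications and postoperative vomiting of grade 2 or higher. They do not remove nausea or somnolence.

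**Illustration of size.** The documents give no event rates, so every rate below is an assumption. Let p be the post-dose risk of an event such as nausea (20% placebo, 50% active), q the probability of a pre-dose record on the dosing date (equal in all arms), and phi the within-subject correlation.

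Tabulated incidence = p + q − P(both), where P(both) = pq + phi × √[p(1−p)q(1−q)].

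With phi = 0 the risk difference is multiplied by (1−q). Without misclassification it is 30 points and the ratio is 2.5.

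| phi | q | Placebo | Active | Difference (points) | Ratio |
|---|---|---|---|---|---|
| 0 | 5% | 24.0% | 52.5% | 28.5 | 2.19 |
| 0 | 10% | 28.0% | 55.0% | 27.0 | 1.96 |
| 0 | 20% | 36.0% | 60.0% | 24.0 | 1.67 |
| 0.2 | 5% | 22.3% | 50.3% | 28.1 | 2.26 |
| 0.2 | 10% | 25.6% | 52.0% | 26.4 | 2.03 |
| 0.2 | 20% | 32.8% | 56.0% | 23.2 | 1.71 |

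Worked case, phi = 0.2 and q = 10%. For placebo, P(both) = 0.02 + 0.2 × √(0.16 × 0.09) = 0.02 + 0.024 = 0.044, so incidence is 0.30 − 0.044 = 0.256. For active, P(both) = 0.05 + 0.2 × √(0.25 × 0.09) = 0.05 + 0.03 = 0.08, so incidence is 0.60 − 0.08 = 0.52.

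Positive correlation inflates each arm less than independence does, but the risk difference shrinks slightly more.

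In subjects, at 15 per arm and phi = 0, the expected counts without misclassification are 3.0 and 7.5 (difference 4.5). They become 4.2 and 8.25 at q = 10% (difference 4.05) and 5.4 and 9.0 at q = 20% (difference 3.6). The difference moves by 0.45 to 0.9 of a subject. Across 45 subjects, q = 10% means 4.5 people with a pre-dose record and q = 20% means 9.

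**The case against.** The strongest reply is that Protocol 6.2.6.1 already sends pre-dose events to medical history. It is the only sentence that says where they are filed; the others can be read as saying when collection starts. Subjects are inpatients, and Table 2 schedules an AE assessment before the Day 1 dose, so most pre-dose events should be elicited then. On that reading few records are left for the date rule to misclassify.

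This could make q small, but it does not remove the problem. The sentence depends on the time of report, so an event that began at 05:00 and was reported after an 08:00 dose still becomes a TEAE. It also sits beside sections and a Table 2 column that have sites collecting AEs from consent and at Day 1 baseline. The TEAE count would then depend on which instruction a site follows.

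Several other points stand:

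- Hours of clock time are not event frequency.
- The illustrated shift is under one subject per contrast.
- Safety is descriptive (Protocol 8.5.4, SAP 8.2.3), no arm is favoured, and the rule errs toward counting more events. The by-relationship table and listings partly reveal such cases, although the overall table does not.
- Protocol 6.2.6.1 speaks of monitoring and is not a formal TEAE definition, though it plainly implies dosing as the start.
- If the eCRF has no onset time, the data support only a date rule until a field is added.

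**Conclusion.** The concern holds. The SAP rule, applied as written, tabulates as treatment-emergent any AE record with onset in about 3 h to 12 h 10 min before the drug was given, contrary to the start point in the protocol. That window follows from the protocol's own times, reading the block stop as 03:00. The expected effect is higher TEAE incidence in every arm and a diluted active-placebo contrast, assuming pre-dose events are balanced by randomization. The size cannot be known from the documents: it depends on unstated event rates and on which recording instruction sites follow. Under the assumed rates it is a loss of 1.5 to 6 points from a 30-point difference with phi = 0, and 1.9 to 6.8 points with phi = 0.2, for q from 5% to 20%. No formal test is affected. This should be corrected, but it does not threaten the primary analysis.

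**What to change.** 1. In SAP 7.3.2 and 8.2.4, define a TEAE as an AE with onset, or worsening of an event already present, at or after the date and time of the first dose (Time 0). The worsening clause is needed because a time-based onset rule alone would drop events that began before the dose and became worse after it.
2. State that an event on the dosing date with missing onset time counts as treatment-emergent. This keeps the conservative default, and only events with a documented pre-dose onset leave the table.
3. Capture AE onset time for the inpatient days if the eCRF does not already do so. The documents do not say, and the SAE report contents in Protocol 6.2.6.8 list only the date of onset.
4. Reconcile Protocol 6.2.6.1 with 6.2.6, 6.2.6.8, 7.2.1 and Table 2 on whether events before the first dose are AEs or medical history. If they are AEs, show them in a separate pre-dose listing.

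The cost is two SAP sentences, one protocol or CRF-guideline clarification, minor programming, and possibly one eCRF field. Settle it before database lock and unblinding, because later reclassification of AEs would be open to question.

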3.2 Safety Assessments

Safety assessments will include the evaluation of AEs, physical and oral examinations, vital sign measurements, pulse oximetry, and 12-lead ECGs. Clinical laboratory tests will be performed at Screening only.

The safety endpoints are the incidence of treatment-emergent adverse events (TEAEs), physical and oral examination findings, and changes in vital signs, pulse oximetry, and ECG measurements.

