8.2.3 Analysis of Safety Data

The safety population is the population for all safety assessments. No imputation will be used in the safety assessments. No inferential statistics are planned. No formal inferential analyses will be conducted for safety variables.

For continuous variables data will be summarized by treatment using n, mean, SD, minimum and maximum values. For categorical variables data will be summarized by treatment using frequency and percentage.

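### SAP 7.3.2 gives two conflicting rules for an adverse event with no start date, and each misclassifies some events that stopped on or before the first-dose date

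*SAP*

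**What the plan says.** SAP 7.3.2 tabulates only treatment-emergent AEs and classifies them by date alone: "Treatment-emergent is defined as AEs with start date" on or after the date of first dose. The stop date plays no part in that test.

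The section then gives two rules for a start date of which nothing is known.

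- **Rule 1:** "If AE start date is completely missing, the date of first treatment administration will be taken as the start date of the event". No condition is attached.
- **Rule 2d**, listed among the rules for partially missing dates: "If all day, month and year parts of the start date are missing, the start date will be estimated" as the first-dose date, "provided that the stop date is either after the date of first treatment administration or completely missing". If that condition fails: "Otherwise, the start date will be estimated to be the first day of the same year as the stop date".

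The SAP does not say which of the two takes precedence. SAP 8.2.3 adds a general sentence: "No imputation will be used in the safety assessments".

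Two protocol passages decide whether such an event can reach the AE data. Section 6.2.6 says "Adverse events will be collected from the time the subject signs an informed consent through the Follow-up visit". Section 6.2.6.1 sends AEs reported before dosing to the medical history instead.

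**The concern.** A date with day, month and year all missing is a completely missing date, so rules 1 and 2d address the same case. If they are applied in order, rule 1 catches every such event and 2d is never reached. If 2d is applied, rule 1 is contradicted. Two programmers working faithfully from the same SAP could therefore produce different treatment-emergent counts.

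Rules 2a to 2d all look at the stop date before assigning the first-dose date. Rule 1 is the only AE start-date rule that does not, and so the only one of these rules for a missing start date that can assign the first-dose date to an event already recorded as over. Safety compared with placebo is a secondary objective, and the AE tables contain treatment-emergent events only, so the rule decides what is counted.

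**Working it through.** The plan states no figure to reproduce. The check is to apply both rules literally to an AE with no start date and then apply the treatment-emergent test.

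**Inputs**

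- Rule 1: start = first-dose date (SAP 7.3.2).
- Rule 2d: start = first-dose date if stop > first-dose date or stop is missing; otherwise 1 January of the stop year (SAP 7.3.2).
- Test: treatment-emergent if start ≥ first-dose date (SAP 7.3.2).
- First-dose date: 15 November 2016, assumed for illustration.

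| Recorded stop date | Rule 1: start, status | Rule 2d: start, status |
|---|---|---|
| 16 Nov 2016 (after first dose) | 15 Nov 2016, emergent | 15 Nov 2016, emergent |
| Missing | 15 Nov 2016, emergent | 15 Nov 2016, emergent |
| 15 Nov 2016 (day of first dose) | 15 Nov 2016, emergent | 1 Jan 2016, not emergent |
| 14 Nov 2016 (day before) | 15 Nov 2016, emergent, start later than stop | 1 Jan 2016, not emergent |

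**Reading the table**

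1. The rules agree in the first two rows. They part only when the stop date is on or before the first-dose date.
2. In the last row rule 1 is wrong. An event that ended before any study drug was given is counted as emergent, and the record has a start after its stop.
3. In the third row rule 2d can be wrong. A short event that began after dosing and ended the same day is moved to 1 January and drops out of the tables.
4. The third-row result has one exception. With first dose on 1 January 2017 and a stop on the same day, 2d returns 1 January 2017 and the event is emergent. With first dose on 2 January 2017 and a stop on that day, 2d returns 1 January 2017 and the event is not emergent.

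**Check of the repaired rule**

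Change the 2d condition to stop ≥ first-dose date, or missing.

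- If stop ≥ first dose: start = first-dose date ≤ stop, so the event is emergent and the dates are in order.
- If stop < first dose: start = 1 January of the stop year ≤ stop < first dose, so the event is not emergent and the dates are in order.
- If stop is missing: start = first-dose date, so the event is emergent.

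No branch gives a start later than the stop, and the result no longer depends on whether first dose fell on 1 January.

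**Size per subject**

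The planned arm is 15 subjects (protocol 8.3). One subject is 1/15 = 6.7 percentage points if all 15 are treated. SAP 8.2.4 counts a subject once at each level of summary, so a row changes only if the subject has no other qualifying event in it.

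**The case against.** The strongest case against is that the situation will seldom arise. It needs a wholly unknown start date together with a stop date on or before first dose. Protocol 6.2.6.1 keeps AEs reported before dosing out of the AE data. Subjects are inpatients from the morning of surgery to Day 3, so staff see most of the relevant window. Partially missing stop dates are moved to the end of the month or year under SAP 7.3.2, which usually puts them after first dose, where the rules agree. All of this stands, and it limits the size. It does not close the route. The 6.2.6.1 provision depends on when an event is reported, so it does not cover an event that ended before dosing and was reported afterwards. Protocol 6.2.6.8 starts AE reporting at consent, and 7.2.1 has AEs recorded before surgery, so some pre-dose events may be entered as AEs anyway.

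A second objection is that rule 1 errs on the safe side, because it never drops an event. That is right for events that stopped on the dosing day, and it is why keeping 2d unchanged would be a poor repair. It does not excuse counting an event that ended before first dose.

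Two stronger readings are tempting, and the documents do not support either.

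- A reader might infer that SAP 8.2.3 supplies a third answer, leaving the event unclassifiable. Its sentence is unqualified, and SAP 3.2 does count AEs as safety assessments: "Safety assessments will include the evaluation of AEs, physical and oral examinations, vital sign measurements, pulse oximetry, and 12-lead ECGs". But it opens a general section on summarising variables. It fits with SAP 8.2.9, which leaves out subjects whose change from baseline is undefined. It is most naturally read as referring to measured values, with the specific date rules of 7.3.2 governing dates. The wording needs clarifying, but it is not a third rule.
- A reader might infer that the outpatient diary will feed this conflict. Events experienced after discharge on Day 3 have a stop date after first dose or none at all, and in both cases rules 1 and 2d give the same result.

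**Conclusion.** The inconsistency is real and lies in the current text of SAP 7.3.2. It is confined to AEs with no start date whose stop date is on or before the first-dose date. Within that set, rule 1 is wrong for events that stopped before first dose. Rule 2d is wrong for events that began after dosing and stopped the same day, apart from the 1 January exception.

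The effect is probably small. The documents give no frequency of missing start dates, so the number of affected events cannot be estimated. The 6.7 points is a ceiling for one subject in one row of a fully treated 15-subject arm, not a forecast. Nothing here supports a claim that the AE tables as a whole would be unreliable. The case for acting is that the treatment-emergent count should follow one rule, settled before unblinding.

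**What to change.** In SAP 7.3.2:

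1. Delete rule 1.
2. Move 2d out of the list for partially missing dates and make it the only rule for a fully missing start date.
3. Change its condition to a stop date *on or after* the first-dose date, or completely missing. Make the same change in 2a to 2c, so that all of them match the ≥ in the treatment-emergent definition.

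In SAP 8.2.3, add that the no-imputation statement does not apply to the date rules in 7.3.2.

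The cost is a few lines of SAP text and no new data. There is one small downside: an event with no start date that ended on the dosing day before dosing would be counted as treatment-emergent. That is conservative, and it matches how the date-only definition already treats an event with a known start on that day.
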